#### Visit 5 (Day 33 [+/- 1 day])

- Photographs
- Blinded-Investigator Evaluation of Treatment Side Effects
- Subject Evaluation of Side Effects Scale
- Review Con Meds
- Review Adverse Events

# Visit 6 (Day 35 [+/- 1 day])

- Photographs
- Blinded-Investigator Evaluation of Treatment Side Effects
- Subject Evaluation of Side Effects Scale
- Review Con Meds
- Review Adverse Events

#### Visit 7 (Day 60[+/- 3 days])

- Pregnancy Test (If applicable)
- Photographs
- Blinded-Investigator Evaluation of Treatment Side Effects, CR-SMFRS and SMSLG
- Subject Evaluation of Side Effects Scale
- Treatment #3 with either Kybella(TM) alone or varying doses of TMC
- Review Con Meds
- Review Adverse Events

#### Visit 8 (Day 63 [+/- 1 day])

- Photographs
- Blinded-Investigator Evaluation of Treatment Side Effects
- Subject Evaluation of Side Effects Scale

- Review Con Meds
- Review Adverse Events

### Visit 9 (Day 65 [+/- 1 day])

- Photographs
- Blinded-Investigator Evaluation of Treatment Side Effects
- Subject Evaluation of Side Effects Scale
- Review Con Meds
- Review Adverse Events

## Visit 10 (Day 90[+/- 5 days])

- Photographs
- Blinded-Investigator Evaluation of Treatment Side Effects, CR-SMFRS and SMSLG
- Subject Evaluation of Side Effects Scale
- Review Con Meds
- Review Adverse Events

#### Visit 11 (Day 180[+/- 5 days])

- Photographs
- Record Subject weight
- Blinded-Investigator Evaluation of Treatment Side Effects, CR-SMFRS and SMSLG
- Subject Evaluation of Side Effects Scale
- Subject Satisfaction Rating Scale
- Review Con Meds
- Review Adverse Events

An exit form will be completed at the final examination, or whenever the patient completes or leaves the study for any reason.

#### 6.4 STUDY ENDPOINT CRITERIA

## A. Subject Completion of Study

If a subject has completed the final visit (Visit 180) of the study, they are considered to have completed the study.

# B. Subject Discontinuation

**Each subject may voluntarily discontinue** the study at any time they choose. Subjects who cannot complete the study for administrative reasons (e.g., non-compliance, failure to meet visit schedule, etc.) will be discontinued from the study. These patients will be asked to return for completion of visit 11.

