# 1. Background and Rationale

Submental fat accumulation is a common concern amongst patients presenting for a cosmetic dermatologic consultation. Liposuction was employed previously for aesthetic improvement. However, alternative non-invasive techniques such as cryolipolysis, focused ultrasound, radiofrequency, and injectable sodium deoxycholate (SDOC) have been developed to meet the increasing demand for minimal downtime procedures. Patient experience with SDOC has been less than optimal, however, with approximately only 1 in 4 patients returning for more than one treatment.

Subcutaneous pure synthetic SDOC (KybellaTM, Allergan) gained FDA approval for reduction of submental fat in June 2015. When injected into submental fat, Kybella(TM) ultimately results in focal adipocytolysis and focal destruction of fat cells. An excellent pharmacokinetic safety profile has been demonstrated, with no measurable increases in serum cholesterol, triglycerides, or free fatty acids detected 24 hours following injection [1, 2]. Furthermore, four large phase III clinical trials to date have demonstrated the efficacy of Kybella(TM) in the reduction of submental fat [3].

Despite the documented safety and efficacy of Kybella(TM), many patients experience a variable degree of edema and pain following subcutaneous injection which can sometimes last for several days to weeks and can be a significant cause for concern. The mechanism of edema and pain secondary to Kybella(TM) injection is unknown but *thought to be an irritant response directly related to deoxycholate and not subsequent adipocyte lysis and death*. This edema and pain is thought to be a major factor contributing to the relatively small percentage of patients returning to complete the full treatment regimen. This study proposes to answer the question of whether immediate swelling and pain can be reduced to increase patient tolerance and improve patient experience without reducing the longer term low level inflammatory component which results in visible and measurable submental fat reduction.

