# 3. Study Design

This is a two-site randomized, double-blind comparison trial of Kybella(TM) injections with or without triamcinolone acetate for the reduction of submental fat. 30 subjects will be enrolled into the trial (15 subjects per site). At each site, 5 will be randomized to receive Kybella(TM) injections alone whereas 10 will receive Kybella(TM) plus differing doses of triamcinolone acetate in the following way:

- 1. Group 1 (5 patients per site): Kybella(TM) alone: 2 mg/cm^2 of Kybella(TM) with **0.2 mL** of 1% lidocaine with no epinephrine plus 0.2cc saline to the non-TMC group to maintain equal concentrations in each injection so that the final Kybella concentration per vial will be 10mg/1.2mls or 1.6mg per 0.2 cc injection point will be delivered in up to 50 injections spaced 1.0 cm apart at 0.2 mL/injection for a total maximal dose of up to 100 mg of SDOC.
- 2. Group 2 (10 patients per site): Kybella(TM)+TMC at **1.0 mg/mL**: 2.0 mL of 2 mg/cm^2 of Kybella(TM) will be mixed with **0.2 mL of 10 mg/mL** of triamcinolone acetate, **0.2 mL of 1% lidocaine with no epinephrine** and then delivered in up to 50 injections spaced 1.0 cm apart at 0.2 mL/injection for a total dose of up to 100 mg of SDOC using a 30 gauge (or smaller) 0.5-inch needle. The final Kybella concentration per vial will be 10mg/1.2mls or 1.6mg per 0.2 cc injection point

The treatment area will be bounded superiorly by a line 1 cm inferior to the mandibular margin, laterally by the sternocleidomastoid muscles, and inferiorly by the hyoid bone. The subjects and evaluating investigator will be blinded to the treatment, thus maintaining double-blind status. By nature of the varying volumes of injection, the treating investigator will be unblinded to the treatment. A series of 3 injection sessions will be performed spaced 4 weeks apart. No lidocaine will be injected prior to injections to prevent further dilution of injected KybellaTM as it will be

premixed with KybellaTM. Chilling with cold will be the method of pain reduction for needle insertion.

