#### C. Subject Termination

A study subject will be terminated if the subject develops signs or symptoms of moderate to severe irritation or any severe adverse event that may be related to the study protocol. A subject will receive appropriate treatment at the discretion of the investigator and will be terminated

from using the treatment regimen. Notification of termination will be clearly documented on the appropriate Case Report Form. These subjects are considered to have completed the study and will not be replaced.

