# E. Study Completion

The study will be complete when 30 subjects have completed Visit 11 or have been terminated from the study.

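### Section 6.4 B ends rating follow-up for subjects who miss the visit schedule, except for Visit 11, and the completion rule in 6.4 E has no slack for a leaver who misses that visit

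*Combined protocol and SAP*

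**What the plan says.** Section 6.4 B (Subject Discontinuation) lets a subject leave voluntarily at any time and then sets a rule for administrative reasons: "Subjects who cannot complete the study for administrative reasons (e.g., non-compliance, failure to meet visit schedule, etc.) will be discontinued from the study". It continues: "These patients will be asked to return for completion of visit 11". No other visit is requested after discontinuation.

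Three neighbouring provisions decide who counts as complete:

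- Section 6.4 A: "If a subject has completed the final visit (Visit 180) of the study, they are considered to have completed the study".
- Section 6.4 C covers subjects taken off treatment for moderate to severe irritation or a possibly related severe adverse event: "These subjects are considered to have completed the study and will not be replaced".
- Section 6.4 E: "The study will be complete when 30 subjects have completed Visit 11 or have been terminated from the study".

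On numbers, Section 3 states "30 subjects will be enrolled into the trial (15 subjects per site" and "At each site, 5 will be randomized to receive Kybella(TM) injections alone whereas 10 will receive Kybella(TM) plus differing doses of triamcinolone acetate".

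On why patients fail to come back, Section 1 reports "approximately only 1 in 4 patients returning for more than one treatment" for the marketed product and says that edema and pain are thought to be a major factor.

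Section 14 (Data Analysis) lists the scales and a significance threshold of 0.05. It names no analysis set and no method for missing ratings.

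**The concern.** The working hypothesis in Section 2 is about immediate edema and immediate pain. These are rated 3 and 5 days after each injection session. A rule that takes a subject out of the study for failing the schedule stops those ratings from that point. The one visit still requested falls at Day 180, when acute swelling and pain from any session can no longer be observed.

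If attendance were unrelated to how a subject felt, this would cost only precision. The protocol's own background gives reason to doubt that. If swelling and pain keep people away, and if triamcinolone reduces swelling, the two arms could lose different kinds of subject at different rates. The remaining ratings would then no longer compare the groups as randomised. With 10 subjects in Group 1, a few such losses matter.

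The completion rule raises a second problem. It requires as many counted subjects as are enrolled, and it does not say what happens when a discontinued subject never attends Visit 11. Only terminated subjects are expressly not replaced. A site trying to satisfy the rule could add a subject, with nothing in the plan saying how that subject would be allocated or analysed.

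**Working it through.** **1. The plan's own number.** 2 sites × (5 + 10) = 30 enrolled, split 10 (Group 1) and 20 (Group 2). This reproduces the stated 30. Section 6.4 E also requires 30, so the slack is 30 − 30 = 0.

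**2. What Visit 11 recovers (Section 6 visit list).** Side effects are rated at Visits 2 to 11, which is 10 visits. Six of these are acute: Visits 2, 3, 5, 6, 8 and 9 (Days 3, 5, 33, 35, 63 and 65). The fat scale is scored on Days 1, 30, 60, 90 and 180. The last injection is at Day 60, so Visit 11 comes 180 − 60 = 120 days later. It recovers final fat, laxity and satisfaction scores, but no acute rating.

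| Discontinued after | Acute visits lost | Side-effect visits lost if Visit 11 attended | Fat scores lost if Visit 11 attended |
|---|---|---|---|
| Visit 3 (Day 5) | 4 of 6 | 7 of 10 (Visits 4–10) | 3 (Days 30, 60, 90) |
| Visit 6 (Day 35) | 2 of 6 | 4 of 10 (Visits 7–10) | 2 (Days 60, 90) |

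**3. Weight of one loss.** Group 1: 1/10 = 10% of the arm. Group 2: 1/20 = 5%.

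**4. Who counts toward the 30.**

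| Subject | Counted? | Source |
|---|---|---|
| Attends Visit 11, whether or not discontinued earlier | Yes | 6.4 A, 6.4 E |
| Terminated for irritation or a severe adverse event | Yes, and not replaced | 6.4 C, 6.4 E |
| Discontinued, not terminated, misses Visit 11 | No, on the plain reading | No rule stated |

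Only the last row creates a shortfall.

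**5. Size of the shortfall.** The documents give no discontinuation or return rate, so both are assumed here. Let d be the probability of discontinuation without termination, and r the probability that a discontinued subject attends Visit 11. Then q = d(1 − r) is the probability of being uncounted. Treating subjects as independent, the expected number uncounted is 30q, the probability that all 30 are counted is (1 − q)^30, and the enrolment needed is 30/(1 − q), rounded up.

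| d | r | q | Expected uncounted | P(all 30 counted) | Enrolment needed |
|---|---|---|---|---|---|
| 5%, 10% or 20% | 100% | 0 | 0 | 1 | 30 |
| 5% | 50% | 0.025 | 0.75 | 0.468 | 31 |
| 10% | 50% | 0.05 | 1.5 | 0.215 | 32 |
| 20% | 50% | 0.10 | 3.0 | 0.042 | 34 |
| 5% | 0% | 0.05 | 1.5 | 0.215 | 32 |
| 10% | 0% | 0.10 | 3.0 | 0.042 | 34 |
| 20% | 0% | 0.20 | 6.0 | 0.001 | 38 |

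If every discontinued subject returns for Visit 11, there is no counting problem at any d. Otherwise a modest rate is enough to make it likely. The last column shows only what the rule would imply if taken literally. It is not a recommendation to enrol more.

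**The case against.** The case on the other side is strong on several points.

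- **Counting.** A reader might infer that discontinued subjects are left out of the count and that 30 can be reached only by replacement. The documents do not support this. Discontinued subjects are asked back for Visit 11 and count if they attend, and no section provides for replacing anyone. The shortfall is confined to leavers who are not terminated and do not return.
- **Tolerability.** A reader might infer that the worst-tolerating patients are removed through 6.4 B. They have their own route in 6.4 C, which counts them and does not replace them. What remains is that a subject who stays away because of pain may never be assessed under 6.4 C, and would then appear as a voluntary leaver or a missed schedule.
- **Trigger.** A reader might infer that one out-of-window visit leads to discontinuation. Section 6.4 B applies to subjects who cannot complete the study, with schedule failure as an example. It sets no threshold, so the number of subjects affected cannot be calculated from the visit windows.
- **Evidence of bias.** The 1-in-4 figure describes experience with the product, not trial attendance, and the link to pain is stated only as thought to hold. A subject who leaves before the second session may already have complete Day 3 and Day 5 ratings for the first.
- **Wording of 6.4 E.** Section 6.4 C ends the treatment regimen, whereas 6.4 E speaks of termination from the study. The latter could be read to cover any exit, which would remove the shortfall. That reading is possible, but 6.4 B and 6.4 C treat discontinuation and termination as separate categories, and the plan should not depend on it.

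None of this restores the interim ratings that 6.4 B gives up, and Section 14 does not say how their absence is handled.

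**Conclusion.** Two points stand.

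First, 6.4 B gives up interim ratings that could be kept. For a subject discontinued after the first session's ratings, that is four of the six acute visits and three interim fat scores. The loss may be related to outcome and may differ between arms. That inference rests on the background statement in Section 1, and the documents establish neither direction nor amount. Each affected subject in Group 1 is 10% of the arm.

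Second, 6.4 E has no slack. On its plain reading it cannot be met without adding a subject once any non-terminated leaver misses Visit 11. Under the assumed range, the probability that all 30 are counted runs from 1 (all return) to 0.001 (20% discontinued, none return). With 10% discontinued and half returning it is 0.215.

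The sponsor should change the wording. The documents do not show that the comparison will be biased, or that replacement is planned.

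**What to change.** **Section 6.4 B.** Record a missed or out-of-window visit as a protocol deviation, not as grounds for ending follow-up. Invite subjects who stop injections to all remaining scheduled rating visits, not only Visit 11.

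**Section 6.4 E.** Define completion as all 30 randomised subjects having completed Visit 11, been terminated or otherwise left. State that no randomised subject is replaced and that all are analysed in their assigned group. Section 14 should repeat the last statement.

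Rules on when injections stop are unchanged.

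**Cost.** The change is wording in Sections 6.4 and 14, plus some already-scheduled rating visits for subjects who would otherwise have left. No extra subjects are needed. Some subjects will decline the visits, so the change reduces the missing ratings but does not eliminate them. For subjects no longer being injected, later ratings describe outcome under assignment, not the reaction to a further session.

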#### C. Subject Termination

A study subject will be terminated if the subject develops signs or symptoms of moderate to severe irritation or any severe adverse event that may be related to the study protocol. A subject will receive appropriate treatment at the discretion of the investigator and will be terminated

from using the treatment regimen. Notification of termination will be clearly documented on the appropriate Case Report Form. These subjects are considered to have completed the study and will not be replaced.

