Canfield Vectra 3D imaging will be performed at baseline and final visit (Appendix C) with analysis and calculation of volumetric changes performed at baseline and final visit. Photos will also be taken with the Intellistudio at all other visits. Follow up visits will be performed 3 and 5 days after each injection session to assess for side effect and tolerability profile. After the final injection session, additional follow up visits will be performed at days 90 and 180 to assess for efficacy. Subject weight will be recorded at baseline and at end of study.

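### Section 6.4 C stops subjects for reactions that can overlap the edema and pain outcomes and does not ask them back, so Day 90 and Day 180 efficacy data can be lost by reaction severity

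*Combined protocol and SAP*

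**What the plan says.** The stopping rule in Section 6.4 C is mandatory: "A study subject will be terminated if the subject develops signs or symptoms of moderate to severe irritation or any severe adverse event" (the event need only be possibly related to the protocol). The subject is then terminated "from using the treatment regimen". On status the section says: "These subjects are considered to have completed the study and will not be replaced".

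The neighbouring sections read differently. 6.4 A defines completion as having done the final visit. 6.4 B, on subjects discontinued for administrative reasons, adds: "These patients will be asked to return for completion of visit 11". 6.4 C has no such sentence. 6.4 E closes the trial as follows: "The study will be complete when 30 subjects have completed Visit 11 or have been terminated from the study". The Visit 11 entry in Section 6 states: "An exit form will be completed at the final examination, or whenever the patient completes or leaves the study for any reason".

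On efficacy, Section 3 says that after the last session "additional follow up visits will be performed at days 90 and 180 to assess for efficacy". It also says "Canfield Vectra 3D imaging will be performed at baseline and final visit", with volume change calculated at those two visits. Section 4.2 b collects satisfaction on Day 180 only. Section 14 names no analysis population and no rule for missing data.

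**The concern.** Two features combine.

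First, the trigger can overlap the outcomes. Section 1 describes the edema and pain after injection as an irritant response. Section 7.1 lists both as possible adverse events. Grade 4 on the scales in Appendices A and B is labelled severe, and grade 3 of edema, tenderness and subject-rated pain and swelling is labelled moderate. A bad enough outcome score can therefore be what ends treatment.

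Second, nothing in 6.4 C keeps such a subject in follow-up. The completed status, the exit form and 6.4 E all allow the subject to leave at that point.

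Days 90 and 180 carry the Section 2 hypothesis that TMC does not impair long-term fat reduction. Final volume and satisfaction have no planned interim value to stand in for them. If TMC reduces reactions as hypothesised, controls would be stopped at a higher rate, in an arm of only 10. Ratings never collected cannot be recovered by later analysis.

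**Working it through.** The plan gives no termination rate, SD, margin or power figure, so there is no figure of its own to reproduce. The arm sizes agree: 2 x 5 = 10 controls, 2 x 10 = 20 TMC, 30 in total (Section 3).

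**1. Limits from the documents alone.** Entry grade is 2 or 3 (Section 4.3) on a 0-4 scale (Appendix A). An unseen Day 180 rating therefore leaves a 4-grade span of possible change.
- Per missing control: 4/10 = 0.4 grade on the arm mean.
- Per missing TMC subject: 4/20 = 0.2 grade.
- Two controls and one TMC subject missing: 4 x (2/10 + 1/20) = 1.0 grade undetermined in the arm difference. If worsening is ruled out (span 2 to 3), this is 0.5 to 0.75.

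These are worst-case limits for any missing rating from any cause. They show how fragile arms of 10 and 20 are; they do not estimate the effect of 6.4 C.

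**2. Illustrative model. Every input is assumed.**
- Only grade 4 triggers the rule.
- Share at grade 3 or above per session, control/TMC: 50/20, 40/20, 30/10 and 20/10%. Grade cut-points are 1 SD apart on a latent scale.
- Within-subject correlation across sessions: 0.4 to 0.8.
- Fat reduction = 0.4 grade x sessions received + 0.7 x (r x reactivity + sqrt(1 - r^2) x noise), with r = -0.5, 0 or 0.5 and no true TMC effect.

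Stopped at any session: 0.6 to 3.4 of 10 controls and 0.5 to 1.7 of 20 TMC subjects (1.1 to 5.1 of 30).

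**3. Fat difference, TMC minus control; positive favours TMC.**

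| Comparison | Result (grade) |
|---|---|
| Rated subjects only, r = -0.5 to 0.5 | about -0.10 to +0.10 (0.00 at r = 0) |
| All randomised, every Day 180 rating obtained | +0.02 to +0.13 |
| First minus second | -0.23 to 0.00 |

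In this model every never-stopped subject has had three sessions, so the first row reflects selection alone. Its sign follows r, the relation between reactivity and fat response. The second row reflects sessions alone: at 0.4 grade per session, +0.02 to +0.13 corresponds to 0.02/0.4 = 0.05 up to 0.13/0.4 = 0.33 fewer sessions per control on average.

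The third row already contains the second. At r = 0 it runs from -0.13 to -0.02, which is the second row with its sign reversed.

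**4. Scale and precision.** Standard error with nobody lost: 0.7 x sqrt(1/10 + 1/20) = 0.27. The largest rated-only error is 0.10/0.27, under 0.4 of a standard error. If all stopped subjects go unrated, the standard error is multiplied by:
- low end: sqrt(1/9.4 + 1/19.5) / sqrt(1/10 + 1/20) = 1.03
- high end: sqrt(1/6.6 + 1/18.3) / sqrt(1/10 + 1/20) = 1.17

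**The case against.** The best defence is that 6.4 C ends treatment, not attendance. Its wording is "from using the treatment regimen", and Sections 4.2 and 6 schedule the Day 90 and Day 180 assessments with no exception for terminated subjects. This stands as a possible reading. It does not settle the matter, because 6.4 E speaks of termination from the study as an alternative to Visit 11, and 6.4 B shows that the protocol asks for a return visit when it wants one.

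The trigger may also be narrower than it looks. Section 13 defines only serious adverse events, so severe in 6.4 C may have been meant that way. Expected reactions may not have been meant to count at all, since the scales are scored up to grade 4 after every session. On either reading few subjects would be stopped. Section 13 does require clinical follow-up after a serious event, but not efficacy ratings.

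A reader might go further and infer that 6.4 C forbids follow-up. It does not: the text is ambiguous, and the completed status and 6.4 E tilt it the wrong way. A reader might also take the -0.23 grade in the working as a bias from lost data that adds to the unequal-sessions shift. It is only the distance between two analyses, and the plan does not choose between them.

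Nor do the documents fix the direction of any bias. Section 1 ties fat reduction to a longer-term inflammatory component and treats the immediate irritant response as separate. Heavier loss among controls is itself an inference from the hypothesis and from the earlier higher-dose study; TMC effects such as steroid atrophy could push the other way.

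**Conclusion.** The point holds as an ambiguity that should be fixed before enrolment. Followed as written, the plan can lose Day 90 and Day 180 efficacy data according to reaction severity, because no sentence asks terminated subjects to return and two sections let them leave.

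The expected size is modest. Under the assumed grade 4 trigger and rates, the rated-only fat difference departs from a true zero by about -0.10 to +0.10 grade against a standard error of 0.27, in a direction that cannot be known in advance. Precision falls by a factor of up to about 1.17. If expected reactions do not trigger the rule, little is lost.

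Full follow-up does not make the comparison neutral. If controls are stopped more often, the all-randomised difference moves by +0.02 to +0.13 grade in favour of TMC because controls receive fewer sessions. That matters where the question is whether TMC does harm. Swelling and pain ratings after session 1 are essentially unaffected; those after sessions 2 and 3 can be missing selectively.

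Confidence is moderate: the reading of the text is firm, but every rate is assumed.

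**What to change.** **Section 6.4 C.** State that termination stops injections only. State that these subjects are asked to attend the remaining scheduled visits, including Day 90 and Visit 11 (Day 180), unless they withdraw. Count them as completers only if Visit 11 is done, in line with 6.4 A.

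**Section 6.4 E.** Amend to match, so that termination of injections does not stand in for Visit 11.

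**Section 14.** Report terminations, sessions received and missing Day 180 ratings by arm. Show Day 180 fat for all randomised subjects by assigned arm, alongside sessions received, and note that unequal sessions can favour TMC and mask harm. Do not score swelling or pain as 0 for sessions that were not given.

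**Cost.** A few sentences. No safety rule is relaxed, the investigator can still stop injections, and no visit is added. A few subjects (about 1 to 5 of 30 under the assumed rates) would attend visits already on the schedule after their injections stop, and some may decline. Which grade counts as irritation is a clinical decision and can be settled separately.
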